We hypothesize that QuitBot will be cost-effective vs. SmokefreeTXT (SFT), as measured by cost per quitter, cost per life year gained, and cost per quality-adjusted life year (QALY) gained. Analyses: We will use current good practices of estimating cost-effectiveness [114], as applied to smoking cessation interventions [115]. To examine whether QuitBot costs less than SFT to help a person quit, we will estimate the incremental cost-per-quitter: difference in total cost of delivering the two interventions [116] divided by the difference in the number of 30-day abstinent participants at 12-months (Total CostQuitBot – Total CostSFT/# AbstinentQuitBot – # AbstinentSFT). Total cost assessments are described in Section C.5.5. Second, to estimate whether QuitBot represents good value vs. SFT per life year gained [115], we will calculate the standard metric of cost per life year gained as: Total CostQuitBot – Total CostSFT/# Life Years AddedQuitBot – # Life Years AddedSFT). Life years added attributable to each intervention's 12-month primary endpoint effect size will be derived from the life years estimates, reported in Stapleton & West [115], that conservatively account for gender, age, discounting, relapse, and unaided cessation. Lastly, to examine whether QuitBot represents good value vs. SFT per QALY [116], an additional analysis of the cost-per-QALY gained will be conducted as: (Total CostQuitBot – Total CostSFT)/(QALYQuitBot – QALYSFT). This analysis will be calculated by adding a Generalized Linear Model-based weighted quality of life parameter derived from the standard EQ-5D quality of life measure [96] taken at the 12-month endpoint. For the cost per life year and cost per QALY analyses, we will assess cost-effectiveness relative to implied willingness to pay in the U.S. of \$100,000 [117]. In each of the three analyses, we will conduct probabilistic sensitivity analyses with 5,000 Monte Carlo simulations that will derive a cost-effectiveness plane (and 95% CI ellipse) across a range of total costs and effect sizes [118]. Similar cost-effectiveness analyses will be conducted for these subgroups: biological sex (male vs. female), age (50 or older vs. 49 or younger), race/ethnicity (non-Hispanic white vs. all other races), and education (high school or less vs more than high school). All will adjust costs to 2019 U.S. dollars and discount future costs and benefits incurred after one year at 3% per annum as is recommended by the panel on cost-effectiveness [105, 119].

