### 11.7 Randomization

We will use computer generated randomly permuted block randomization. Participants and outcome assessors will be blind to random assignment throughout the entire duration of the trial. Randomization will be stratified on biological sex (male vs. female), heaviness of smoking index score ( $\leq 4$  vs  $>4$ ), and percent confidence in being smoke-free in 12 months ( $\leq 70\%$  vs.  $>70\%$ ).

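### Cost per quitter is defined from arm totals and head counts, so in the age, race/ethnicity and education subgroups chance differences in arm size distort the ratio

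*Combined protocol and SAP*

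**What the plan says.** All of this is in the combined protocol and SAP.

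- **Cost per quitter (section 11.3).** The numerator is the "difference in total cost of delivering the two interventions", and this is "divided by the difference in the number of 30-day abstinent participants at 12-months". The printed formula repeats it with arm totals and numbers abstinent.
- **Cost per life year (section 11.3).** The numerator is the same total-cost difference. The denominator is printed as a number of life years added, but the text explains it thus: "Life years added attributable to each intervention's 12-month primary endpoint effect size will be derived from the life years estimates".
- **Cost per QALY (section 11.3).** The ratio is "Total CostQuitBot – Total CostSFT)/(QALYQuitBot – QALYSFT". The text does not say whether the QALY terms are arm totals or means.
- **Subgroups (section 11.3).** "Similar cost-effectiveness analyses will be conducted for these subgroups: biological sex (male vs. female), age (50 or older vs. 49 or younger), race/ethnicity", and education.
- **Randomization (section 11.7).** "We will use computer generated randomly permuted block randomization". "Randomization will be stratified on biological sex (male vs. female), heaviness of smoking index score" and confidence in being smoke-free. Age, race/ethnicity and education are not stratification factors.

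No section gives a mean cost per participant for these ratios, or rescales the arms to a common size. Unit costs are referred to a Section C.5.5 that is not part of the document.

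**The concern.** A difference in totals over a difference in counts equals the per-person contrast only when both arms hold the same number of people, apart from one special combination of costs and quit rates. Blocked 1:1 randomization secures near-equality for the whole trial and within sex. Within age, race/ethnicity and education, arm sizes are left to chance. The written rule then books extra people in an arm as extra cost and as extra quitters.

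Objective 3 is meant to inform payors and policymakers about value. A subgroup ratio that moves with the allocation split could suggest a difference in value between subgroups where none exists per person. Sampling error in the quit rates is expected in any such estimate. This component comes from the definition and can be removed.

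**Working it through.** **Inputs from the document.** 1,647 randomized 1:1 (section 11.1); projected quit rates pQ = 13.9% and pS = 9.3% (section 11.5); minority goal of at least 30% (section 6.0); 43% with high school education or less in the pilot (section 2.3). **Assumptions.** SmokefreeTXT cost cS = $20 per person, QuitBot cost cQ = $22 to $40 per person, and cost proportional to people in the arm.

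**The plan's own figure.** The plan states no cost-effectiveness ratio, but the sample size behind its quit rates can be reproduced. With pooled variance, two-sided alpha 0.05 and 80% power:

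n = [1.96·√(2·0.116·0.884) + 0.842·√(0.139·0.861 + 0.093·0.907)]² / 0.046² ≈ 760 per arm, as stated.

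**Algebra.** Let K be the subgroup size and d = nQ − nS.

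- Written numerator: nQ·cQ − nS·cS = (K/2)(cQ − cS) + (d/2)(cQ + cS)
- Written denominator: nQ·pQ − nS·pS = (K/2)(pQ − pS) + (d/2)(pQ + pS)

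The first term of each is the per-person contrast times K/2. The second is the arm-size error. As relative errors:

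- numerator: (d/K)·(cQ + cS)/(cQ − cS)
- denominator: (d/K)·(pQ + pS)/(pQ − pS) = (d/K)·0.232/0.046 = 5.04·d/K

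The ratio is right only if d = 0 or the two multipliers are equal, that is cQ/pQ = cS/pS.

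**Size of d.** With the number of subgroup members in the QuitBot arm hypergeometric (823 of 1,647 in that arm):

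- 30% subgroup, K = 494: SD(d) = 2·√(823·0.30·0.70·824/1646) = 18.6. Denominator error SD = 5.04·18.6/494 = 19%. It exceeds 10% in 63% of draws. Equal arms would give 247·0.046 = 11.4 extra quitters.
- 43% subgroup, K = 708: SD(d) = 20.1. Denominator error SD = 5.04·20.1/708 = 14%. It exceeds 10% in 46% of draws.

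**Worked split, 30% subgroup.**

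- 257 vs 237, costs $25 and $20: (6,425 − 4,740)/(35.72 − 22.04) = 1,685/13.68 = $123. The per-person ratio is 5/0.046 = $109.
- 237 vs 257, same costs: 785/9.04 = $87.
- Costs $22 and $20: per-person 2/0.046 = $43. The rule gives 914/13.68 = $67 or 74/9.04 = $8.

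**Error in the ratio, 30% subgroup.** The last two columns add binomial sampling of the quit outcomes.

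| QuitBot cost (SFT $20) | Numerator multiplier (denominator 5.04) | Median error, arm size alone | Median error with sampling, per-person rule | Median error with sampling, written rule |
|---|---|---|---|---|
| $22 | 42/2 = 21 | 40% | 38% | 60% |
| $25 | 45/5 = 9 | 10% | 38% | about 40% |
| $30 | 50/10 = 5 | about 0% | 38% | about 38% |
| $40 | 60/20 = 3 | 5% | 38% | about 38% |

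At $22 the written ratio, from arm size alone, has the wrong sign in about 11% of draws.

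**Whole trial.** At 823 vs 824 (d/K = 1/1,647) the error is largest at $22: (21 − 5.04)/1,647 ≈ 1%. At the other assumed costs it is smaller.

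**Life years and QALYs.** If the denominator comes from an effect size or a mean, it carries no arm-size error, and the numerator error stands without offset. A total over a per-person quantity would also mix scales, even with equal arms. The text does not settle which case applies.

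**The case against.** The strongest reply is that this is notation. The formulas are written for the whole trial, where they are harmless. The subgroup analyses are only described as similar, and section 11.3 commits to current good practice, so analysts may well use means. Section 11.5 says the probabilistic sensitivity analyses draw on the Objective 1 confidence intervals, which come from a logistic model. The effect side of the simulations is therefore at least partly off the head-count scale already. Some cost of a digital program may be fixed and not proportional to arm size, which would change the numerator error. And with quitters this few, sampling noise dominates: even the per-person difference in quitters is zero or negative in about 5% of draws in the 30% subgroup.

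Most of this stands as a limit on size. It does not remove the point: the only definition on the page is in totals and counts, and nothing tells the programmer to depart from it.

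Three stronger readings are tempting, and the documents do not support them:

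- *All three ratios carry the imbalance in both terms.* Only cost per quitter has a literal head-count denominator. Life years come from an effect size, and the QALY terms are not said to be totals.
- *The denominator figures (SD 19%, over 10% in 63% of draws) are the error in the ratio.* They are not. The numerator moves in the same direction and can offset them almost fully, as at $30.
- *Apparent subgroup differences in value would be mainly artefacts of arm size.* Under most of the assumed costs they would come from small numbers of quitters.

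**Conclusion.** The point holds for cost per quitter in the age, race/ethnicity and education subgroups. Followed literally, the stated rule makes the ratio depend on the chance split of people between arms. For cost per life year and cost per QALY, the total-cost numerator is affected, and the scale of the denominator must be stated to match it. The overall result and the sex subgroups are not materially at risk.

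The arm-size and denominator figures rest only on the plan's numbers and the assumed subgroup shares. The ratio error also rests on unit costs absent from the document and on cost scaling with arm size. It is negligible at some cost combinations, and serious mainly when the per-person cost gap is small relative to the costs themselves. It is worth correcting because the error is avoidable, not because it would dominate the results.

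**What to change.** In section 11.3, define all three ratios, overall and in every subgroup, as the difference in mean cost per randomized participant (QuitBot minus SmokefreeTXT) divided by the difference in proportion abstinent, or in mean life years or mean QALYs per randomized participant. State that the cost side of the 5,000 Monte Carlo simulations uses the same per-participant scale as the effect inputs drawn from Objective 1.

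This is a short wording change. It needs no new data, does not materially change the overall result, and has no evident drawback. It will not make the subgroup ratios precise, so they should still be read with their simulation intervals.

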### 3.3 Study Design

We will conduct a fully-powered two-arm parallel randomized controlled trial comparing QuitBot to SmokefreeTXT (SFT). Based on evidence from text messaging trials meta-analyses [1], we will stratify randomization on biological sex (male vs. female), heaviness of smoking index score ( $\leq 4$  vs  $>4$ ), and percent confidence in being smoke-free in 12 months ( $\leq 70\%$  vs.  $>70\%$ ). Moderators will be measured at baseline, mediators at 3 and 6 months post randomization, and cessation and cost-effectiveness outcomes at 3, 6, and 12 months post randomization.

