### 10.1 Source Data to be Recorded Directly

There are 6 sources of data for the study: (1) screening survey (2) baseline survey, (3) contact form, (4) 3-month follow-up survey, (5) 6-month follow-up survey, and (6) 12-month follow-up survey. We will also collect automated utilization data from the QuitBot CA program, Google Analytics, and SmokefreeTXT program. All data will be collected directly from consenting adult participants. A description of these sources of data follows.

**Survey Data.** The Baseline Survey, hosted on our secured recruitment website, will collect data on (1) demographics, (2) nicotine and tobacco use, (3) nicotine dependence, (4) readiness to quit, (5) quit attempts, (6) smoking costs, (7) quality of life, (8) interpersonal trust, (9) social support, and (10) contact information needed for the study's follow-up data collection activities – as well as information about whether or not it is acceptable to receive email or voice messages and mail from

the study. The 3-month survey will primarily collect data on intervention processes (e.g., therapeutic alliance), cessation progress (e.g., quit attempts) and outcomes (e.g., 30-day abstinence), and the participant's experiences with their assigned smoking cessation intervention. The 6- and 12-month surveys will primarily collect data on cessation progress/outcomes.

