### 11.2 Primary/Secondary Endpoints/Hypotheses and Analytical Methods

[figure not shown]
The primary endpoint will be biochemically-verified 30-day point prevalence at 12 months post randomization. Secondary endpoints will be 30-day biochemically confirmed point-prevalence at 3 and 6 months post randomization. Consistent with remote digital cessation study methods [1, 18], biochemical confirmation will be conducted on participants self-reporting no smoking at all in the last 30 days.

Our primary outcome hypothesis is that QuitBot will have significantly higher 30-day point prevalence abstinence at 12 months post-randomization than SmokefreeTXT. For each comparison of the treatment arms on the primary and all secondary endpoints, we will use a logistic regression model. Using standard smoking cessation trial intent-to-treat analysis, all missing outcomes will be coded as smokers [31, 35-39]. The model will adjust for all stratification factors as well as baseline factors that are imbalanced after randomization and significantly related to the outcome. In addition, we will conduct these sensitivity analyses: (1) multiple imputation of missing outcomes [107-109], (2) complete case analysis of those providing follow-up data, (3) using a secondary cessation outcome of no use of cigarettes and other nicotine or tobacco products except FDA-approved nicotine replacement therapies, (4) adjusting for baseline usage of other tobacco and nicotine products, and (5) adjust for usage of other interventions and cessation medications after study enrollment.

[figure not shown]

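### The cost-per-QALY analysis uses 12-month EQ-5D and states no adjustment for baseline quality of life, so chance imbalance stays in the denominator if arm-specific utilities are used

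*Combined protocol and SAP*

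**What the plan says.** Section 11.3 defines cost per QALY as the difference in total cost divided by the difference in QALYs, written as "QALYQuitBot – QALYSFT". The QALY term is obtained by "adding a Generalized Linear Model-based weighted quality of life parameter", and that parameter is "derived from the standard EQ-5D quality of life measure [96] taken at the 12-month endpoint". The section gives no covariates, link function or weights. It mentions no change score and no area-under-the-curve calculation.

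Three other places bear on this:
- Section 10.1 lists the baseline survey items, including "6) smoking costs, (7) quality of life, (8) interpersonal trust". It does not name the baseline quality-of-life instrument.
- Section 3.3 (repeated in 11.1) plans to measure "cessation and cost-effectiveness outcomes at 3, 6, and 12 months post randomization". For EQ-5D, section 11.3 names only the last of these times ("taken at the 12-month endpoint").
- Section 11.2 has the only covariate rule for a treatment comparison: "The model will adjust for all stratification factors as well as baseline factors that are imbalanced after randomization and significantly related to the outcome". It belongs to the cessation models, introduced by "For each comparison of the treatment arms on the primary and all secondary endpoints, we will use a logistic regression model", and is not extended to the QALY analysis.

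**The concern.** Utility at baseline is usually a good predictor of the same person's utility a year later. If the arms differ by chance at baseline, part of that difference reappears at 12 months. An unadjusted comparison of 12-month utilities counts it as an intervention effect.

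This matters here because the true difference is likely to be very small: only the extra quitters contribute to it, and each by a modest amount. It is also the denominator of a ratio that section 11.3 judges against $100,000, so noise can change the ratio's size or sign. With the covariates left open, an adjusted or an unadjusted denominator could also be chosen after the data are seen.

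**Working it through.** **Inputs from the documents.** Section 11.5 gives projected quit rates of 13.9% and 9.3%, two-sided alpha 0.05, 80% power and 85% response at 12 months. The objectives give 823 per arm.

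**Assumptions, not in the documents.** EQ-5D utility SD 0.15 to 0.25, equal at baseline and 12 months; baseline to 12-month correlation r of 0.5 to 0.8; utility gain per quitter 0.02 to 0.10. The calculation treats the QALY term as an arm difference in mean 12-month utility.

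**The plan's own figure.** For two proportions with pooled variance under the null and mean rate 0.116:

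n = [1.960 × √(2 × 0.116 × 0.884) + 0.842 × √(0.093 × 0.907 + 0.139 × 0.861)]² / 0.046² = 760 per arm.

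This matches Table 3, so the 4.6-point difference is the planned effect. The plan gives no precision or sample-size figure for the QALY analysis.

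**Expected difference in mean utility.** 0.046 × gain per quitter:
- 0.046 × 0.02 = 0.0009
- 0.046 × 0.05 = 0.0023
- 0.046 × 0.10 = 0.0046

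**Participants with 12-month data.** 823 × 0.85 ≈ 700 per arm.

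**Noise.** The SE of the unadjusted difference is SE = SD × √(2/700). The part carried over from baseline imbalance has SD r × SE. After adjustment for baseline, the SE is SE × √(1 − r²).

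| SD | Unadjusted SE | Carried-over part, r = 0.5 to 0.8 | Adjusted SE, r = 0.5 to 0.8 |
|---|---|---|---|
| 0.15 | 0.0080 | 0.0040 to 0.0064 | 0.0069 to 0.0048 |
| 0.20 | 0.0107 | 0.0053 to 0.0086 | 0.0093 to 0.0064 |
| 0.25 | 0.0134 | 0.0067 to 0.0107 | 0.0116 to 0.0080 |

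**Ratio of carried-over imbalance to expected difference.** From 0.0040/0.0046 ≈ 0.9 to 0.0107/0.0009 ≈ 12.

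**Middle case (SD 0.20, r = 0.7, gain 0.05).** The imbalance is 0.7 × 0.0107 = 0.0075 against 0.0023, a ratio of about 3. At $100,000 per QALY, counting the difference for one full year, that is about $750 of noise against $230 of benefit per participant.

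**Gain from adjustment.** The variance falls by r²: 25% at r = 0.5, 49% at 0.7 and 64% at 0.8.

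**What adjustment does not do.** The chance that the denominator has the wrong sign is Φ(−difference/SE). In the middle case it falls from 41.5% to 38.2%. With a gain of 0.10 per quitter it falls from 33.3% to 27.3%.

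**Sensitivity of the signal.** The projected rates count non-responders and unverified quitters as smokers. If they are scaled up for the 85% response and 80% verification completion, the difference is 4.6/(0.85 × 0.80) = 6.8 points. The utility difference is then 0.0014 to 0.0068, and the ratio runs from about 0.6 to 8. The conclusion is the same.

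**The case against.** The strongest reply concerns what the QALY term is. The sentence about the EQ-5D parameter follows the life-year analysis, which applies published life-year estimates to the quit effect. It can be read as placing a quality weight on those modelled life years. With one common weight, a baseline difference between arms largely cancels. With arm-specific weights it stays, and would be magnified over the life years. The text does not settle this, so this reply stands and the point is conditional on it.

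Several stronger readings are tempting but not supported:
- A reader might infer that the plan rules out baseline adjustment. It does not: it names a model and lists no covariates, and the 12-month wording says when the outcome is measured. What can be said is that no adjustment is stated.
- A reader might set the full SE of the baseline difference at 823 per arm (0.010 at SD 0.20) against the expected difference and call the noise 2 to 11 times the signal. Only r times that SE carries into the 12-month comparison, and about 700 per arm will have 12-month data.
- A reader might infer a systematic bias. Allocation is randomized, so the harm is lost precision and bias conditional on the imbalance that happens to occur.
- A reader might infer that the omission decides Objective 3. Cost per quitter and cost per life year use no EQ-5D, and most of the imprecision in cost per QALY comes from the small expected difference.

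It is also fair to object that the data are not confirmed. Section 10.1 does not name the baseline instrument and does not list quality of life among the main content of the follow-up surveys. EQ-5D at 3 and 6 months may not exist.

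**Conclusion.** The point holds in a conditional and moderate form. The plan states no baseline adjustment for the EQ-5D parameter, collects quality of life at baseline, and has no other rule that would bring the baseline value in. If arm-specific 12-month utilities form the QALY difference, chance baseline imbalance of 0.004 to 0.011 (one SD) remains in a denominator expected to be 0.001 to 0.005. Adjustment would remove that conditional bias and cut the variance by about 25% to 64%.

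Every utility input behind these figures is an outside assumption. After adjustment the SE at SD 0.20 is still 0.0064 to 0.0093, above the whole expected range, so the cost-per-QALY estimate would remain imprecise. Under a common weight on modelled life years there is little left to correct beyond saying so. The primary endpoint and sample size are not affected.

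**What to change.** In section 11.3:
1. State that the EQ-5D model includes arm, baseline EQ-5D utility and the three stratification factors (sex, heaviness of smoking index, confidence). If the baseline instrument is not the EQ-5D, use the baseline quality-of-life score as the covariate instead.
2. Take the arm-specific utilities, or the QALY difference, from that model.
3. Say whether the weight is arm-specific or common to both arms, and how it enters the QALY calculation.
4. Confirm whether EQ-5D is collected at 3 and 6 months, and reconcile 11.3 with 3.3 and 11.1. Use area-under-the-curve QALYs only if those values exist and a baseline utility is available.

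The cost is a few sentences and one covariate from data already planned, with no change to sample size or to the cessation analyses. The wording should be settled before utilities are compared by arm.

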
**Analysis of Sex as a Biological Variable:** Consistent with NIH guidelines [120], we will report data by sex, in order to the consider the potential influence of sex in the interpretation of study results. Specifically, for all the analyses described above, we will examine the estimated difference in effect sizes between men and women by incorporating interactions between treatment and sex in a regression model, or by separately analyzing results by sex. We will also stratify random assignment by sex.

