11.5 Sample Size and Power

We determined sample size for binomial proportions aimed at 80% power for Primary Objective 1 using the following parameters: (1) randomized to one of the two interventions; (2) conservative 12-month outcome survey response rate of 85%, based on our most recently published large RCT comparing two digital interventions [84]; (3) 80% completion rate of biochemical verification [103, 104]; (4) intent-to-treat analysis where, as standard in digital intervention smoking cessation trials, all those with missing data (including missing biochemical data) are coded as smokers [1, 121]; and (5) two-sided test with  $\alpha = .05$ . We adjusted all power analyses for expected non-response rates and biochemically-confirmed cessation rates so that outcomes would not be inflated.

Power for Objective 1: Objective 1 will compare 12-month quit rates between QuitBot vs. SFT. Projected quit rates at 12-month follow-up were conservatively calculated using (1) quit rates at 3-month follow-up in our pilot RCT, along with (2) well-established relapse curves, which provide a data-derived estimate (i.e., 20-35%) of the rate of decay of intervention effects by 12-month follow-up [90, 91, 122]. We estimated a relapse of 27% (between 3 and 12 month-follow-up) and survey response and biochemical verification completion rates of 85% and 80%, respectively. The 12-month quit rate for SFT is conservatively estimated as 9.3%, as consistent with the projected SFT 12-month relapse rates from the pilot RCT and the 8.4% average quit rate from the most recent meta-analyses [1, 2, 18-21]. As shown in Table 5, obtaining 80% power to significantly detect a quit rate as low as 13.9% for QuitBot (vs. 9.3% for SFT) requires 1,520 randomized participants, with 760 in each study arm.

Table 3. Objective 1 Sample Size Estimates.

	Projected relapse rate				
	20%	25%	27%	30%	35%
	QuitBot 12-month follow-up 30-day point prevalence quit rate				
	15.2%	14.3%	13.9%	13.3%	12.4%
Total in each arm	484	653	760	983	1,579
Total randomized	968	1,306	1,520	1,966	3,158

This very conservatively estimated 13.9% quit rate would have high public health impact—49% higher impact than the projected 9.3% quit rate for SFT and 65% higher than the average 8.4% quit rate observed in text messaging interventions [1, 2, 18-21].

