Power for Objective 2: Statistical power for testing the serial mediation of therapeutic alliance and engagement measures for smoking cessation was estimated based on the following: (1) conservative estimates of the post treatment standardized effect size for each hypothesized mediator (i.e., a small effect size of .14 [123]; (2) two-sided test with  $\alpha=.05$ ; and (3) 85% follow-up rate for mediator data collection. Conservatively, power calculations do not account for any increased power from covariate adjustment (e.g., stratified randomization factors). The PROCESS analysis method (described in Section C.7.2) uses the percentile bootstrap method to estimate the indirect effect, which provides high power while still maintaining an accurate type-I error rate [124]. For even a small three-path mediation effect (e.g.,  $0.01 \leq a_1d_{21}b_2 < 0.05$ ), according to Taylor et al. [124], a total sample size of 1,000 will attain statistical power of 99%, while power to detect larger mediation effect approaches 1. In addition, Fritz [113] showed that a sample size of 558 provides 80% power to detect small indirect effects passing through one mediator (e.g.,  $a_1b_1 = 0.02$ ). Thus, a sample size of 1,520 in this trial, with 85% follow-up, will provide high power (>99%) to detect at least small three-path and two-path mediation effects of therapeutic alliance and engagement measures.

Power for Objective 3: Statistical power is not an explicit consideration in cost-effectiveness analysis, but probabilistic sensitivity analyses will draw from model input distributions based on 95% CIs in Objective 1. Given the power in Objective 1 outcomes, we expect to obtain precise estimates of in-trial cost-effectiveness in Objective 3.

The last objective is exploratory so no power analysis was conducted.

Power for Sex as a Biological Variable: We will compare quit rates between QuitBot and SmokefreeTXT in the male and female subgroups. With 1,520 participants, and an expected ratio of 60% female:40% male, we expect to randomize 912

females and 608 males to the study. Given these sample sizes, and assuming a 9.3% 12-month quit rate for SmokefreeTXT, the minimum detectable odds ratios with 80% power are 1.78 for females and 2.00 for males.

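### Section 11.3 lets a sex difference be judged by separate analyses in men and women, which do not test a difference, and Section 11.5 gives power only for those within-sex comparisons

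*Combined protocol and SAP*

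**What the plan says.** The paragraph on sex as a biological variable in Section 11.3 sets the aim and its scope: "for all the analyses described above, we will examine the estimated difference in effect sizes between men and women". It then gives two ways to do so: by a treatment-by-sex interaction in a regression model, "or by separately analyzing results by sex". It has no rule for choosing between them and does not say which one decides.

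The matching power paragraph in Section 11.5 describes only the second way: "We will compare quit rates between QuitBot and SmokefreeTXT in the male and female subgroups". It expects 912 women and 608 men and, "assuming a 9.3% 12-month quit rate for SmokefreeTXT", reports that "the minimum detectable odds ratios with 80% power are 1.78 for females and 2.00 for males". It gives no figure for the interaction.

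Section 11.4 is also relevant. It names sex as an example of a demographic moderator and specifies a logistic model for 12-month abstinence with arm, moderator and their product. That analysis is labelled exploratory, and Section 11.5 says no power analysis was done for it.

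**The concern.** The question asked is whether the effect differs between men and women. Two separate arm comparisons, one per sex, each ask whether there is an effect in that sex. Setting the two results side by side is not a test of the difference, least of all when the subgroups are unequal in size and neither is well powered at the planned effect. Under one common effect, the larger subgroup will often reach significance when the smaller does not, and sometimes the reverse.

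At stake is how the sex results are read. Section 2.3 wants moderators to show who benefits most and least, so a chance split between the sexes could be taken as guidance on whom to offer the intervention. The primary comparison and the sample size are not affected.

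**Working it through.** **Inputs.** From Section 11.5: 9.3% quit rate for SmokefreeTXT, 13.9% for QuitBot, two-sided alpha 0.05, missing outcomes counted as smoking (so the rates already carry non-response), 912 women and 608 men. From Section 11.1: 1:1 allocation, hence 456 per arm in women and 304 in men. The tests below are unadjusted.

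**Step 1: reproduce the plan's figures.** For n per arm, the pooled two-proportion test has power

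Φ{[d − 1.96·√(2p̄(1−p̄)/n)] / √[(p₁(1−p₁)+p₂(1−p₂))/n]}.

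- With 9.3% and 13.9% the formula requires 760 per arm, or 1,520 in total, exactly as stated. The other four columns of Table 3 also match (484, 653, 983 and 1,579 per arm).
- The odds ratio detectable with 80% power is 1.775 at 456 per arm and 1.992 at 304 per arm. At the stated 1.78 and 2.00, power is 0.804 and 0.805. The stated figures are sound as within-sex figures.

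**Step 2: power in each sex at the planned effect.** The planned odds ratio is (0.139/0.861)/(0.093/0.907) = 1.574; d = 0.046 and p̄ = 0.116.

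- Women: (0.046 − 1.96 × 0.02121)/0.02115 = 0.21, power 0.583.
- Men: (0.046 − 1.96 × 0.02597)/0.02591 = −0.19, power 0.425.

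**Step 3: chance that exactly one sex is significant.** The sexes are independent samples.

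- Women only: 0.583 × (1 − 0.425) = 0.335.
- Men only: 0.425 × (1 − 0.583) = 0.177.
- Exactly one: 0.335 + 0.177 = 0.512. Both: 0.248. Neither: 0.239.

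A binomial simulation of 400,000 trials gave 51.1% for exactly one sex. In the same trials the interaction test rejected in 5.0%, its nominal rate. At 1,647 enrolled, assuming the same 60:40 split (about 494 and 329 per arm), power is 62% and 45%, and exactly one sex is again significant in 51%.

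**Step 4: dependence on the common effect (1,520 participants).**

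| Common odds ratio | Women | Men | Exactly one sex |
|---|---|---|---|
| 1.0 | 5% | 5% | 10% |
| 1.2 | 13% | 10% | 20% |
| 1.3 | 23% | 17% | 32% |
| 1.5 | 48% | 35% | 50% |
| 1.574 (planned) | 58% | 42% | 51% |
| 1.78 | 80% | 63% | 42% |
| 2.0 | 93% | 80% | 24% |
| 2.18 | 98% | 90% | 12% |

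The planned effect lies close to the peak.

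**Step 5: what the interaction can detect.** The variance of the log ratio of odds ratios is the sum of 1/[n·p(1−p)] over the four sex-by-arm groups:

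1/38.46 + 1/54.57 + 1/25.64 + 1/36.38 = 0.1108, so SE = 0.333.

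- 80% power requires a ratio of exp(2.80 × 0.333) = 2.54. At 1,647 with the 60:40 split, SE = 0.320 and the ratio is 2.45.
- For a ratio of 1.5 (log 0.405), power is about 23% at 1,520 and 24% at 1,647.
- If the odds ratio were 1.78 in women and 1.0 in men, the interaction would have about 38% power at 1,520.

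**The case against.** The strongest reply is that Section 11.4 already commits to an interaction test for sex on 12-month abstinence. A reader might infer from Sections 11.3 and 11.5 alone that no such test is planned, and that would be wrong. This narrows the point but does not remove it. Section 11.4 is exploratory, covers one time point, and does not say that it overrides Section 11.3. The alternative in Section 11.3 therefore still stands for the 3- and 6-month endpoints, the sensitivity analyses, mediation and cost-effectiveness. For 12-month abstinence there are two rules side by side.

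A second reply is that the plan speaks of examining an estimated difference, and sex-specific odds ratios with confidence intervals are a legitimate description. That is right. A reader might infer that the plan will treat significance in one sex only as evidence of a difference, but no section says so. The 51% measures how often a misleading pattern would arise, not how often the plan would make a false claim. The particular pattern of women significant and men not arises in about 34%.

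Third, about half is close to the worst case and holds only near the planned effect, as Step 4 shows. Even so, the 20% at an odds ratio of 1.2 is well above the 5% error rate of an interaction test.

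Fourth, a reader might infer that 1.78 and 2.00 are offered as sensitivity to a sex difference. They are not: Section 11.5 introduces them as comparisons within each sex. What is missing is the figure for the interaction.

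**Conclusion.** The point holds in a limited form. Section 11.3 accepts, as an alternative to the interaction, a method that cannot test its own stated aim, and the only power given for sex belongs to that method. With the planned effect identical in both sexes, about 51% of trials would be significant in exactly one sex (women only 34%, men only 18%, before rounding 33.5% and 17.7%). The interaction has 80% power only for a ratio of odds ratios of about 2.5, so the trial can say little about moderate sex differences.

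These figures assume a 9.3% control rate in both sexes (as Section 11.5 does), unadjusted tests and, for 1,647, a 60:40 split that the documents give only for the planned 1,520. The documents do not support the stronger reading that the plan will declare a sex difference from one-sex significance. They leave that reading open.

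**What to change.** **Section 11.3, cessation outcomes.** Reconcile with Section 11.4. Make the treatment-by-sex interaction, reported as a ratio of odds ratios with 95% CI from the stratification-adjusted logistic model, the sole basis for any statement about a sex difference in cessation at 3, 6 and 12 months. Apply the same rule to the sensitivity analyses of these outcomes. Report sex-specific odds ratios with CIs as description only. Sex is already a covariate in that model as a stratification factor, so this adds one term.

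**Section 11.3, mediation and cost-effectiveness.** A logistic interaction does not serve these. Base any statement about sex on the between-sex difference in the estimate, with its bootstrap interval (mediation) or simulation interval (cost-effectiveness).

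**Section 11.5.** Add that the interaction has 80% power only for a ratio of odds ratios of about 2.5 (2.54 at 1,520; 2.45 at 1,647 if the 60:40 split holds). Note that 1.78 and 2.00 are within-sex figures and do not address a difference.

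**Cost.** Wording only, with no new data and no change to the primary analysis or sample size. Reporting by sex is kept. The downside is that the plan's stated sensitivity to sex differences becomes less favourable.
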